5.0 Inclusion and Exclusion Criteria

5.1 *Describe the criteria that define who will be **included** in your final study sample.*

NOTE: This may be done in bullet point fashion.

Response:

- Caregivers of community-dwelling older adults (55 and over) who are member of the PACE
- Adult 21 years or older
- Living with the care recipient or within a distance so that they can visit him/her minimum once a week
- Cognitively intact (can recall three words immediately and 3 minutes later)
- Competent in English

5.2 *Describe the criteria that define who will be **excluded** from your final study sample.*

NOTE: This may be done in bullet point fashion.

Response:

- Distant caregivers who does not help care recipients' activities of daily living (ADL) or instrumental activities of daily living (IADL).

5.3 *Indicate specifically whether you will include any of the following special populations in your study using the checkboxes below.*

NOTE: Members of special populations may not be targeted for enrollment in your study unless you indicate this in your inclusion criteria.

Response:

- Adults unable to consent
- Individuals who are not yet adults (infants, children, teenagers)
- Pregnant women
- Prisoners

Caregivers may be pregnant. We will not exclude them.

5.4 *Indicate whether you will include non-English speaking individuals in your study. **Provide justification if you will exclude non-English speaking individuals.***

*In order to meet one of the primary ethical principles of equitable selection of subjects, non-English speaking individuals may **not** be routinely excluded from research as a matter of convenience.*

In cases where the research is of therapeutic intent or is designed to investigate areas that would necessarily require certain populations who may not speak English, the researcher is required to make efforts to recruit and include non-English speaking individuals. However, there are studies in which it would be reasonable to limit subjects to those who speak English. Some examples include pilot studies, small unfunded studies with validated instruments not available in other languages, studies with numerous questionnaires, and some non-therapeutic studies which offer no direct benefit.

Response:

One instrument (Positive aspect of caregiving) is only available in English. To fully understand caregivers' challenges and convey solutions, our current study OT graduate students are not competent enough in other languages to provide interventions. We do not have budget to hire interpreters.

6.0 Vulnerable Populations

If the research involves special populations that are considered vulnerable, describe the safeguards included to protect their rights and welfare.

NOTE: You should refer to the appropriate checklists, referenced below, to ensure you have provided adequate detail regarding safeguards and protections. You do not, however, need to provide these checklists to the IRB.

6.1 *For research that involves **pregnant women**, safeguards include:*

NOTE CHECKLIST: Pregnant Women (HRP-412)

Response: Caregivers may be pregnant women. The procedures in the study are such that they present no added risk to the mother or feturs.

N/A: This research does not involve pregnant women.

6.2 *For research that involves **neonates of uncertain viability or non-viable neonates**, safeguards include:*

NOTE CHECKLISTS: Non-Viable Neonates (HRP-413), or Neonates of Uncertain Viability (HRP-414)

Response:

N/A: This research does not involve non-viable neonates or neonates of uncertain viability.

6.3 *For research that involves **prisoners**, safeguards include:*

NOTE CHECKLIST: Prisoners (HRP-415)

Response:

N/A: This research does not involve prisoners.

6.4 *For research that involves persons who have not attained the legal age for consent to treatments or procedures involved in the research (“children”), safeguards include:*

NOTE CHECKLIST: Children (HRP-416)

Response:

N/A: This research does not involve persons who have not attained the legal age for consent to treatments or procedures (“children”).

6.5 *For research that involves cognitively impaired adults, safeguards include:*

NOTE CHECKLIST: Cognitively Impaired Adults (HRP-417)

Response:

N/A: This research does not involve cognitively impaired adults.

6.6 *Consider if other specifically targeted populations such as students, employees of a specific firm, or educationally or economically disadvantaged persons are vulnerable. Provide information regarding their safeguards and protections, including safeguards to eliminate coercion or undue influence.*

Response:

In this study, no participants will be people who require special consideration.

7.0 Eligibility Screening

7.1 *Describe screening procedures for determining subjects’ eligibility. Screening refers to determining if prospective participants meet inclusion and exclusion criteria.*

 *Include all relevant screening documents with your submission (e.g. screening protocol, script, questionnaire).*

Response:

A screening document is included in an invitation letter and is described in 9.0 Recruitment Methods. In addition, when we make a phone call, we will also ask screening question. This is also attached.

N/A: There is no screening as part of this protocol.

8.0 Recruitment Methods

N/A: This is a records review only, and subjects will not be recruited. NOTE: If you select this option, please make sure that all records review procedures and inclusion/exclusion screening are adequately described in other sections.

8.1 Describe when, where, and how potential subjects will be recruited.

NOTE: Recruitment refers to how you are identifying potential participants and introducing them to the study. Include specific methods you will use (e.g. searching charts for specific ICD code numbers, Research Participant Groups, posted advertisements, etc.).

Response:

An invitation letter will be mailed to all caregivers of PACE enrollees who have cognitive impairment from the PACE. (The letter is attached.) Caregivers who are interested in the study will return the letter to the PI.

8.2 Describe how you will protect the privacy interests of prospective subjects during the recruitment process.

NOTE: Privacy refers to an individual's right to control access to him or herself.

Response:

Caregivers who are interested in the study will contact the PI. They will not be able to stop receiving the invitation letter from the PACE, but they control access to them by contacting or not contacting the PI; therefore their privacy is protected.

8.3 Identify any materials that will be used to recruit subjects.

NOTE: Examples include scripts for telephone calls, in person announcements / presentations, email invitations.

 For advertisements, include the final copy of printed advertisements with your submission. When advertisements are taped for broadcast, attach the final audio/video tape. *NOTE: You may submit the wording of the advertisement prior to taping to ensure there will be no IRB-required revisions, provided the IRB also reviews and approves the final version.*

Response:

The invitation letter and a flyer are attached. They will be mailed together.

9.0 Procedures Involved

9.1 Provide a description of **all research procedures or activities being performed and when they are performed once a subject is screened and determined to be eligible. Provide as much detail as possible.**

NOTE: This should serve as a blueprint for your study and include enough detail so that another investigator could pick up your protocol and replicate the research. For studies that have multiple or complex visits or procedures, consider the addition of a schedule of events table in in your response.

Response:

After obtaining approval from the IRB, UB OT graduate students (OTGS) will be educated and trained for 2 months prior to the start of the intervention. They will study the protocol, interview methods, and interventions. PACE rehabilitation, department staff will also be educated

about the protocol and they will mail an invitation letter and a flyer to caregivers of person with dementia. These records are readily available at the PACE as a standard record keeping procedure.

Interested caregivers will contact the PI and will be screened for eligibility for the study.

OTGS will make an appointment to visit participants. While reading a consent form, an OTGS will explain the study in detail and make sure that the caregiver understand the content. Their right to withdraw from the study without penalty will be explained. After obtaining written consent, a structured interview will take place about 30 minutes. It starts with asking demographic questions, care recipient's cognitive and physical function, levels of assistance the caregiver is providing, and followed by questions about caregivers. This section will ask caregiver burden, fatigue, depression, positive aspect of caregiving, and self-efficacy in caregiving.

The OTGS will talk with caregivers to understand problems in depth. Examples may include difficulty in (a) understanding the disease development process and its consequences; (b) assisting care recipient (CR)'s ADL, IADL, and communication; (c) coping with CRs' undesirable behaviors (e.g., non-use of a stair glide, pulling a cord to turn off lights, reluctance in changing clothes and washing hair, inactivity and lack of motivation in daily routine); (d) maintaining caregivers' health and strength; (e) coordination of care among family members, and (f) having own time. In addition, we will specifically address fall prevention because PACE enrollees have a high fall rate.

When the detailed challenges were documented, the OTGS may recommend some solutions, if she has, such as educating the process of Alzheimer's disease and suggesting an assistive device, good grip utensils.

At the end of the interview, the participant will be paid \$20.00.

The UB geriatric team including OTs, a gerontologist, and OTGS will brainstorm to develop solutions to identified problems. Within a week, these solutions will be presented to the participant and the OTGS and the participants will decide final solutions that the participant will perform. We use a caregiver-centered approach to facilitate their motivation to continue their care. The proposed approach will emphasize working collaboratively with caregivers to identify challenges and individualized strategies for each caregiver to solve specific problems. This is a different approach from the traditional therapist-client relationship, in which therapeutic prescriptions are made and provided by OTs to their clients.

Agreed-upon solutions will be reported to the PACE, especially if suggestions involve CRs. If assistive devices are needed, the PACE will provide them along with proper training for use.

Example interventions include: (a) didactic education about diseases; (b) the use of errorless techniques to improve assistance for CR's ADL,

IADL, and communication tasks; (c) the use of incentives (e.g., providing a favorite scented shampoo, going for an ice cream after going to a hair stylist, having a snack or short game to prevent going to bed right after dinner); (d) use of the Buffalo Functional Exercise for strengthening (a home-based exercise developed for PACE by the PI and shown to be effective in preventing falls, as reported by the NY Dept. of Health; attached); (e) use of a schedule/calendar on a computer, cell phone and/or blackboard in CR's home to coordinate caregiving tasks for family members; (f) suggesting more frequent PACE daycare visits or use of a nearby PACE-recommended daycare center; and (g) home safety suggestions using the Home Safety Self-Assessment Tool (HSSAT) to prevent falls in CR's home environment. We expect that more customized solutions will arise from this project.

A month after initial assessment, OTGS will contact CRs for follow-up and 2 months later, the posttest will be administered. At 4 months, follow-up interview will occur. The number of home visits (4-6) will vary depending on case. Finally 6 months after the intervention, a phone call will be made, asking the same questions before and the number of falls and emergency visits of care recipients in the past 10 months. After each interview, a participant will be paid \$20. (The total maximum is \$80).

9.2 Describe what data will be collected.

NOTE: For studies with multiple data collection points or long-term follow up, consider the addition of a schedule or table in your response.

Response:

The outcome measures will use established instruments. To measure caregiver burden, 12-item Zarit Burden Interview (ZBI), for depression, 20-item Center for Epidemiology Study-Depression (CES-D) will be used. Positive Aspect of Caregiving has 9 items. Self-esteem and fatigue questions will use a visual analog scale from 1 to 10. In addition, items of activities of daily living (ADL, e.g., eating, dressing, and toileting) and instrumental ADL (IADL, e.g., meal preparation, housekeeping) that caregivers are assisting will be identified. We do not assess or provide interventions for CRs directly, but we ask caregivers about CR's cognitive levels using Global Deterioration Scale, and functional levels using FIM to assess ADL and OARS' IADL. We also ask if care recipients fell or visited an emergency room.

 *9.3 List any instruments or measurement tools used to collect data (e.g. questionnaire, interview guide, validated instrument, data collection form).*

Include copies of these documents with your submission.

Response:

The assessment form is attached.

9.4 Describe any source records that will be used to collect data about subjects (e.g. school records, electronic medical records).

Response:

We will not use other sources or records. But if the cause of cognitive impairment is not clear, we will ask the PACE to provide it for us. This is written in the consent form.

*9.5 Indicate whether or not **individual** subject results, such as results of investigational diagnostic tests, genetic tests, or incidental findings will be shared with subjects or others (e.g., the subject's primary care physician) and if so, describe how these will be shared.*

Response:

We will share the solutions with caregivers but not the score of outcome measures, unless the score of CES-D is 15 or higher (indicative of depressive symptoms). This will be shared with PACE because their program include not only care recipients but also their caregivers.

*9.6 Indicate whether or not **study** results will be shared with subjects or others, and if so, describe how these will be shared.*

Response:

At the assessment, if a caregiver scores 15 or higher for the CES-D, the interviewer will inform him/her about the result and contact the PI immediately. The PI will report it to the PACE immediately. The PACE will respond to this situation according to their policy. The policy for caregivers is instituted because they are integral part of the care recipient's ability to continue living in the community. Other assessed results will not be shared with participants, but aggregated data will be shared with the PACE. This include problems and solutions.

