16.0 Data Management and Analysis

16.1 *Describe the data analysis plan, including any statistical procedures. This section applies to both quantitative and qualitative analysis.*

Response:

For two hypotheses, we first analyze a linear trend of dependent variables over time. If they are linear, we will use Generalized Estimating Equation to compare the two groups' slopes. A main effect and an interaction effect will be examined. If it is not, we will use Repeated Measures ANOVA with a between-factor. The contrasts within a group and the difference between groups will be performed as post hoc tests. To answer the last research question to find the difference between

the 4-months data and 6 month after intervention (or at 10 months), we will use Repaeated measurs ANVA with a between-factor.

To answer research questions, we will list all challenges for both groups and solutions for the treatment group. The effectiveness of solutions will be evaluated using a Likert Scale (from very effective to not effective at all) and percentages will be reported. For the rate of continued community, living at 4 months will be tabulated for both groups and a chi-square test will be used. The number of falls and emergency visits will be compared for these two groups using Mann Whitney U-test.

The significance level for primary analyses will be set at .05. SPSS 26.0 will be used for statistical analyses.

16.2 If applicable, provide a power analysis.

NOTE: This may not apply to certain types of studies, including chart/records reviews, survey studies, or observational studies. This question is asked to elicit whether the investigator has an adequate sample size to achieve the study objectives and justify a conclusion.

Response:

The sample size for this study was determined by a power analysis based on the study similar to our study (Kamiya et al., 2014). The effect size found in the article was $d = .65$. We will use a directional hypothesis; therefore, we set $\alpha = .05$, and in order to achieve 80% of statistical power, we will need 30 participants in each group, therefore 60 in total. Expecting 25% of attrition, we will recruit 75 participants.

16.3 Describe any procedures that will be used for quality control of collected data.

Response:

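### Falls and emergency visits are compared on unblinded caregiver report alone, while fall prevention is part of the intervention, so reporting may differ by arm in either direction; no baseline count is described to adjust for

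*Combined protocol and SAP*

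**What the plan says.** - **Status of the outcome.** Section 1.2 adds care-recipient falls and emergency visits after the research questions and hypotheses. The endpoint section (2.1) names burden and depression as primary, and positive aspects of caregiving and self-esteem as secondary. Falls are neither.
- **Intervention.** Section 9.1 states that "we will specifically address fall prevention because PACE enrollees have a high fall rate". Its example interventions include "home safety suggestions using the Home Safety Self-Assessment Tool (HSSAT) to prevent falls in CR's home environment" and a home exercise presented as preventing falls.
- **Control.** Section 3.1 gives controls usual support, and 16.1 lists solutions for the treatment group only.
- **Measurement.** Section 9.2: "We also ask if care recipients fell or visited an emergency room", with no time point given. The only timed question is in the final telephone call (9.1), on "the number of falls and emergency visits of care recipients in the past 10 months".
- **Other sources.** Section 9.4: "We will not use other sources or records". The one exception is asking the PACE for an unclear cause of cognitive impairment.
- **Baseline interview.** Section 9.1: "It starts with asking demographic questions, care recipient's cognitive and physical function, levels of assistance the caregiver is providing", then, for the caregiver, "This section will ask caregiver burden, fatigue, depression, positive aspect of caregiving, and self-efficacy in caregiving". Neither part names fall history. The assessment form is attached to the submission but is not in the text available here.
- **Analysis.** Section 16.1: "The number of falls and emergency visits will be compared for these two groups using Mann Whitney U-test". No covariate is mentioned, and no blinding of caregivers or interviewers is described.

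**The concern.** The people whose attention to falls the intervention sets out to change are the people who supply the count. A difference between arms in reported falls is therefore the product of a difference in falls and a difference in reporting, and the plan has no means of telling the two apart. Randomisation does not help, because the difference in reporting arises after allocation. A single recall over 10 months gives it more room.

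Two opposite mechanisms are plausible. Caregivers taught to watch for falls may notice and remember more of them, which could hide a benefit or create an apparent excess. Caregivers who have been helped to prevent falls may play them down, which could create a spurious benefit.

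A second, smaller matter is that without a baseline count the comparison cannot be adjusted for a strong predictor of later falls, nor can balance be checked.

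**Working it through.** **The plan's own figure.** The plan gives no power or sample size for falls. Its 30 per group is for d = 0.65, one-sided 0.05, 80% power: n = 2 × ((1.645 + 0.842)/0.65)² ≈ 29.3, rounded up to 30. This reproduces, and it fixes the 30 per arm used below.

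**Assumptions.** The documents give no fall rate, dispersion or reporting share. All of these are assumed: mean true falls of 1 to 2 per 10 months, between-person coefficient of variation (CV) of 1 (Poisson-gamma counts), 30 per arm, two-sided Mann-Whitney at 0.05, 4,000 simulated trials per case.

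**Step 1: effect of differential reporting on the ratio.** Observed ratio = true ratio × (share reported, treated) / (share reported, control).

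| True ratio | Treated / control reporting | Observed ratio | Rejection rate, mean 1 | Rejection rate, mean 2 |
|---|---|---|---|---|
| 1.00 | 70% / 70% | 1.00 | 5% | 5% |
| 1.00 | 90% / 70% | 0.90/0.70 = 1.29 | 9% | 10% |
| 1.00 | 50% / 70% | 0.50/0.70 = 0.71 | 12% | 14% |
| 0.70 | 70% / 70% | 0.70 | 11% | 14% |
| 0.70 | 90% / 70% | 0.70 × 0.90/0.70 = 0.90 | 5% | 6% |
| 0.70 | 50% / 70% | 0.70 × 0.50/0.70 = 0.50 | 27% | 38% |

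At a mean of 1.5, null rejection is about 9% for 90% vs 70% and about 12% for 50% vs 70%. Power for a true ratio of 0.70 with complete reporting is about 14%.

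**Step 2: chance imbalance in fall history.** The standard deviation of the difference between arm means in fall propensity, relative to the mean, is CV × √(2/30): 0.8 × 0.258 = 0.21 and 1.0 × 0.258 = 0.26. A difference above 25% then occurs in 23-33% of randomisations. The test already allows for this. With 45% prior fallers at three times the rate of others (assumed), simulated null rejection was 5.3%. It rises to about 11% only within those trials that happen to have a gap of 20 points or more in prior fallers, which are about 15% of trials at 40-50% prior fallers.

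**Step 3: what a baseline count would buy.** If propensity persists fully and the baseline count is as long and complete as the follow-up count, the correlation is r = mean × CV² / (1 + mean × CV²).
- Mean 1, CV 0.8: 0.64/1.64 = 0.39.
- Mean 2, CV 1: 2/3 = 0.67.

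The standard-error ratio √(1 − r²) is 0.92 to 0.75, a reduction of 8-25% at most. In simulation under assumed inputs, adjustment raised power from 14% to 17-19% at a true ratio of 0.70, and from 37-38% to 45-53% at 0.50.

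**The case against.** Much can be said for leaving the plan as it is. Falls are an additional outcome without a stated hypothesis. Every reporting share above is assumed. Power is low even with perfect data, so better measurement would not make this comparison decisive. The sentence on fall prevention names no arm: treated-only teaching is inferred from usual support for controls (3.1) and solutions for the treatment group only (16.1). These points stand, and they limit the weight of the concern. They do not remove it, because the plan commits to a between-group test with no caveat about its source.

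Four stronger readings are tempting, and the documents support none of them.

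- **That chance differences in fall history bias the result.** In a randomised comparison they lie within the test's 5% error (Step 2). The loss is precision.
- **That no baseline count will be taken.** None is described, but the fall question in 9.2 is undated and the attached form cannot be seen, so a baseline item is possible.
- **That bias would run towards more reported falls in the treated arm.** Nothing in the documents fixes the direction.
- **That PACE records would be a neutral source.** Section 9.1 has agreed solutions reported to the PACE and allows for suggesting more frequent PACE daycare, so PACE capture may itself differ by arm. Nor do the documents say that the PACE logs falls or how a fall at home would reach its records.

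**Conclusion.** The concern holds as a limitation of an additional outcome. Changed reporting cannot be separated from a true effect on falls, and the bias could go either way. With an assumed 20-point gap in reporting, a true ratio of 0.70 could appear as anything from 0.50 to 0.90, and null rejection rises from 5% to about 9-12% at a mean of 1.5 falls (up to 14% at a mean of 2). The absence of a described baseline count is a separate matter of precision, worth at most about 8-25% of the standard error under favourable assumptions.

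A reader might go further and infer that differential reporting is what stops the trial from answering its falls question. That is not supported: with about 14% power for a ratio of 0.70 under the assumed mean of 1.5 and CV of 1, the comparison is weak whatever the reporting. The primary and secondary endpoints are not affected by this point.

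**What to change.** 1. **Sections 9.1 and 9.2.** At the baseline interview in both arms, ask the same fall and emergency-visit count over a fixed look-back, if the attached form does not already do so. State when the question in 9.2 is asked.
2. **Section 16.1, analysis.** Compare the arms with a model for counts adjusted for the baseline count (for example negative binomial regression), named in advance. Keep the Mann-Whitney test as a sensitivity analysis.
3. **Section 16.1, interpretation.** State that the comparison of falls and emergency visits is exploratory, rests on unblinded caregiver report with bias of unknown direction, and has low power at 30 per arm.
4. **Optional, section 9.4.** If the PACE logs these events, request its records for both arms over the same dates from randomisation, as a supportive check only. Note that PACE capture may differ by arm. This would need wider consent wording and a record request for about 60-75 care recipients.

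Items 1 to 3 cost one added baseline question and slightly more analysis work. The baseline count will carry its own recall error, so the gain will probably fall short of the upper figures above. Adjustment improves precision; it does not remove differential reporting, which is why the statement in item 3 is still needed.

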3.0 Study Design

3.1 Describe and explain the study design (e.g. case-control, cross-sectional, ethnographic, experimental, interventional, longitudinal, observational).

Response:

We will use a qualitative method to understand difficulties that caregivers are facing and to document solutions and their implementation process; and a quantitative method using a randomized contoured trial with pre-, post- and follow-up experimental design. A treatment group will receive a 1 to 2-month interventions to solve caregiving challenges, and a control group will receive usual support. Assessments will be conducted at baseline, 2 months (posttest), 4 months (follow-up), and 6 months post intervention.

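### Section 9.1 lets the student recommend solutions during the baseline interview without limiting this to the treatment group, so control caregivers can receive some intervention content.

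*Combined protocol and SAP*

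**What the plan says.** Section 3.1 describes "a randomized contoured trial with pre-, post- and follow-up experimental design" and sets the contrast: "A treatment group will receive a 1 to 2-month interventions to solve caregiving challenges, and a control group will receive usual support".

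Section 9.1 describes a single sequence for participants: consent, a structured interview containing the outcome questionnaires, and an in-depth talk about caregiving problems. It then says: "When the detailed challenges were documented, the OTGS may recommend some solutions, if she has". Two examples follow: teaching the caregiver about Alzheimer's disease, and pointing to an aid such as easier-to-hold utensils. The next sentence begins "At the end of the interview, the participant will be paid", so the recommending step falls inside the baseline interview. After that come the team discussion and, within a week, a presentation of solutions to the participant. Later in the same section: "Example interventions include: (a) didactic education about diseases". The PACE is to supply assistive devices if they are needed.

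Section 16.1 states the reporting rule: "we will list all challenges for both groups and solutions for the treatment group". Section 9.5 says that solutions will be shared with caregivers and names no arm.

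The supplied text does not say when allocation takes place relative to the baseline interview, or whether the student knows the arm at that point.

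**The concern.** The trial compares an intervention made of individual solutions with usual support. If the student may offer solutions in an interview that both arms attend, some controls can receive part of what is being tested. The student is also well placed to do so, since section 9.1 provides two months of training that covers the interventions.

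The advice comes after the baseline questionnaires, so baseline scores are not affected. The exposure is in the 2-month, 4-month and later comparisons of burden and depression, the two primary outcomes. If the advice helps controls, the between-group difference shrinks. That costs power and understates the effect; it does not raise the type I error. The planned sample size leaves almost no spare power to absorb such a loss.

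**Working it through.** **1. Do controls reach the recommending step?**

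| Place | What it settles | What it leaves open |
|---|---|---|
| 3.1 | Controls get usual support | What happens at the control baseline visit |
| 9.1, baseline interview | The student may recommend solutions before the closing payment | Which arm or arms this covers |
| 9.1, example interventions | Disease education is example (a), so this advice is intervention content | Devices are not in the example list; they appear as something the PACE provides |
| 16.1 | Challenges are listed for both arms, solutions for the treatment arm | Whether a student may advise a control |

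The baseline interview in 9.1 is the only described means of eliciting challenges, and 16.1 needs them from controls. Controls therefore very probably have the same interview. That the optional advice then follows for a control is permitted by the wording, but not stated.

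**2. Reproduce the plan's sample size.** Inputs from section 16.2: d = 0.65, directional test at .05, 80% power.

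Normal approximation: n per arm = 2(z₀.₉₅ + z₀.₈₀)² / d² = 2(1.645 + 0.842)² / 0.65² = 29.3, rounded up to 30. This matches the stated 30 per group.

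Noncentral t check at n = 30: df = 2n − 2 = 58, one-sided critical value 1.672, noncentrality d√(n/2) = 0.65 × √15 = 2.517. Power = 80.0%.

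**3. Illustrate dilution.** Let c be the average share of the full effect that passes to controls. The contrast becomes d(1 − c). The documents give no value for c, so every row below except c = 0 is an assumption.

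| Assumed c | d(1 − c) | Noncentrality, n = 30 | Power, 30 per arm | Power, 28 per arm |
|---|---|---|---|---|
| 0 | 0.650 | 2.517 | 80.0% | 77.5% |
| 10% | 0.585 | 2.266 | 72.4% | 69.7% |
| 20% | 0.520 | 2.014 | 63.5% | 60.9% |
| 30% | 0.455 | 1.762 | 53.9% | 51.4% |

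The last column uses the completers implied by the plan's own recruitment and attrition: 75 × 0.75 = 56.25, or about 28 per arm. The drop from 80.0% to 77.5% in its first row comes from that attrition arithmetic and not from dilution.

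**The case against.** The strongest reply is that no step in 9.1 is labelled by arm. The team discussion, the solutions visit, the devices and the 4 to 6 home visits are all written for the participant. Read literally, controls would get the whole intervention, which 3.1 and 16.1 plainly do not intend. On this view, all solution-giving in 9.1 belongs to the treatment pathway, and the sentence at issue goes with it. The advice is also optional, and one remark after an interview of about 30 minutes is slight beside a 1 to 2-month individual programme.

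Much of this stands. Sections 3.1 and 16.1 do show that solutions are meant for the treatment group. The reply does not dispose of the point, because the advice sits inside an interview that controls very probably share, whereas the later steps are easily read as separate treatment visits. A rule about what will be listed in the analysis does not tell a student what not to say.

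Four stronger readings are tempting, and the documents do not support them:

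- **Controls will be treated.** The text gives a discretionary permission and does not direct advice to controls.
- **Advice to controls would go unrecorded.** Section 16.1 says what will be listed, not what is written down at visits. The assessment form is an attachment outside the supplied text.
- **The power figures forecast the loss.** They rest on assumed dilution, and nothing in the documents suggests that a single piece of advice carries 20% or 30% of the full effect.
- **A null result could not be interpreted.** Attenuation lowers power and pulls the estimate towards zero. That is a limitation to weigh and report, and it does not make the result unreadable.

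**Conclusion.** The point holds as a permitted route to contamination, of known direction and unknown size. Sections 3.1, 9.1 and 16.1 do not agree on whether a control caregiver may be given solutions at the baseline interview, and they must be reconciled. Any leakage would bias the 2-month and later differences in burden and depression towards zero. At the planned 30 per arm, power would fall from 80% to 72% under an assumed 10% dilution and to 64% under 20%; these are illustrations only.

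The conclusion rests on two assumptions: that controls have the same in-depth interview, which 16.1 implies, and that attachments and student training, which are not in the supplied text, do not already bar advice to controls. If they do, only the wording of 9.1 needs correcting.

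**What to change.** In section 9.1:

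- Limit study recommendations to the treatment group, and begin them after the baseline interview, at the solutions visit already scheduled within a week.
- State that allocation is revealed only after the baseline assessment is complete, so that the interview is conducted in the same way in both arms.
- Record any advice given to a control caregiver, so that the extent of contamination can be reported beside the between-group results.

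Carry the same wording into the student training.

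Limiting the present sentence to the treatment group would be a smaller edit, but it works only if the student already knows the arm during the baseline interview. Starting recommendations afterwards avoids that.

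This is a cheap improvement: a few sentences, with no added visit, participant or outcome measure. The downside is that treatment-group advice may start up to about a week later than the present text allows.
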